### 8.1. Study Design

This is a retrospective cohort study using health insurance claims (outpatient and inpatient) data provided by MDV (Tokyo, Japan).

This is a comparative study to investigate the risk of hospitalization due to CAP among COPD patients who were incident users of Trelegy 100 or MITT. HR of hospitalization due to CAP between two groups is estimated by identifying and following patients without the pneumonia event at the index date (at risk). Follow-up period will be up to 360 days in the base-case analysis.

The scheme of the study is shown below.

**Figure1 Study design**

Identification of the study population will be conducted using health insurance claims data (outpatient and inpatient) and Diagnosis Procedure Combination (DPC) data. Patients surveyed are aged 40 years or older at the start date of prescription (index date) for Trelegy 100 or MITT during the 1,080-day identification period (from May 22, 2019 to May 5, 2022).

In this protocol, one month is defined as 30 days based on the manner of Post-marketing Surveillance in Japan.

In this study, data will be collected retrospectively with the 1,080-day identification period to have as much patient data as possible within the time frame to submit study results for the reexamination application for Trelegy 100. We plan to conduct data review in 2022 as described at the bottom of ABSTRACT, and we need time to agree on the protocol with PMDA after the endorsement by Protocol Review Committee (PRC), and thus we prepared this protocol in 2020.

Patients with records of International Statistical Classification of Diseases and Related Health Problems, Tenth Revision (ICD -10) codes for COPD (J42, J43 or J44), one record at the index date and additional 2 records (outpatient visit or hospital admission) in the 360 days look-back period [index date, index date -360 days]. This criterion is to exclude patients with infrequent visits and to secure collection of patient characteristics data in the look-back period.

At least one record (outpatient visit or hospital admission) with any ICD-10 codes in the 180 days

prior to the start date of look-back period [index date – 360 days, index date – 540 days]. This criterion is to secure patient records throughout the look-back period.

Follow-up period will be from the index date (including the index date) to the earliest date of the followings: 1) admission date of hospitalization due to CAP or 2) date of death or 3) end date of exposure period with Trelegy 100 or MITT by discontinuation (defined in 8.3.1.1. continuation of exposure), or 4) 360 days after the index date.

In base case analysis, the 360-day follow-up period will be applied, while the 1,440-day follow-up period will be used in sensitivity analysis.

The reason for the 360-day follow-up period is based on the article by Suissa et al. which demonstrated that the effect of ICS on pneumonia occurrence among COPD patients peaked in the first year of use.

A patient will be censored at the first event of “hospitalization due to CAP” because identification of “time at risk for pneumonia” is feasible for the first event but difficult for the second or subsequent events. For example, if hospitalization due to CAP continued longer than the recovery from CAP by another comorbidities, it is not clear when the patient recovered from CAP during the hospitalization. Namely, “the end date of the current pneumonia” and thus “time at risk for the next pneumonia” cannot be identified.

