### 8.3.1.1. Continuation of exposure

[figure not shown]

Figure3 Exposure period

- 1) Gap (variable): Actual period between 2 consecutive prescriptions
- 2) Grace period (constant): The threshold used to determine if an interruption in therapy causes a patient to be considered non-persistent

Continuation of exposure will be defined by using “prescription period”, “gap” and “grace period” (see Figure3).

Prescription period: Treatment period estimated by dosage in package insert (as described in a separate “statistical analysis plan”)

Gap: Actual period between 2 consecutive prescription periods

Grace period: The threshold used to determine discontinuation of treatment

In this study, we set the “grace period” at 30 days.

If a gap between 2 consecutive prescription periods is 30 days or less, the treatment is considered continuation.

If a gap between 2 consecutive prescription periods is 31 days or more, the treatment is considered discontinuation.

Japan’s medical fee system recommends careful consideration for long-term prescription more than 30 days. Restrictions on prescription period for 14 days right after the launch was not applied to Trelegy 100. Based on these situations, we regarded 30 days as a standard prescription period for both Trelegy 100 and MITT. By considering 30-day prescription, potential delay in physician visits and missing medicine, the grace period was set to 30 days.

Exposure period in follow-up period will be defined as the period starting at the index date and ending at 30 days (grace period) after the end date of the final prescription period\* of Trelegy 100 or MITT during 360 days after the index date. If the final prescription period starts before the end date of the previous prescription period, the overlapped days of the 2 prescription periods will be added to the grace period (30 days) in calculating the end date of the final prescription period.

\*Final prescription period of Trelegy 100 or MITT will be defined as follows:

- 1) Subsequent prescription period of Trelegy 100 or MITT started 31 days or more (longer than grace period) after the end date of the last prescription period. In MITT group, the end date of the last prescription period is the end date of overlapping prescription period.
- 2) MITT includes a variety of combination of ICS/LAMA/LABA, and only the change in components of MITT is not considered discontinuation.

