#### 8.7.3.1. Primary endpoints

##### 8.7.3.1.1. HRs for hospitalization due to CAP among incident Trelegy 100 users compared to incident MITT users

To adjust covariates (refer to “8.3.3.1 Covariates”), propensity score which is defined as a probability of Trelegy 100 treatment selection conditional on observed covariates will be estimated for an individual using logistic regression. Multicollinearity will be considered when selecting covariates. By inverse probability of treatment weighted Cox models using the propensity score, the marginal HR along with 95% confidence intervals will be estimated among incident Trelegy 100 users compared to incident MITT users. Variance estimation will be calculated using robust sandwich variance method.

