#### **8.7.3.3. Sensitivity analysis**

The primary endpoints and explanatory analysis will be performed by the following conditions. When one of the 3 conditions are applied, other 2 conditions will not be applied but original conditions will be kept.

- One of inclusion criteria is changed from “patients with ICD-10 codes for COPD (J42, J43 or J44)” to “patients with ICD-10 codes for COPD (J42, J43 or J44) and with prescription of any inhaled medicine with the indication of COPD”, at the index date and on at least 2 visits (outpatient visit or hospital admission) in the look-back period
- Overlap of 3 components for MITT group is changed from at least 1 day to at least 14 days (including the index date)
- Follow-up period is changed from maximum 360 days to maximum 1,440 days (after the index date)

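### The primary HR censors at discontinuation but weights only for treatment choice, so it can be biased in either direction, and no planned sensitivity analysis tests this

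*Protocol*

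**What the plan says.** - **Follow-up (Protocol 8.1).** It runs from the index date to the first of CAP admission, death, "end date of exposure period with Trelegy 100 or MITT by discontinuation", or 360 days.
- **Stop rule (8.3.1.1).** Common to both groups: "If a gap between 2 consecutive prescription periods is 31 days or more, the treatment is considered discontinuation". One clause is specific to MITT: "In MITT group, the end date of the last prescription period is the end date of overlapping prescription period". One clause softens it: "only the change in components of MITT is not considered discontinuation".
- **Weights (8.7.3.1.1).** The propensity score is described as one "which is defined as a probability of Trelegy 100 treatment selection conditional on observed covariates".
- **Estimator (8.7.3.1.1).** "By inverse probability of treatment weighted Cox models using the propensity score", "the marginal HR along with 95% confidence intervals will be estimated among incident Trelegy 100 users compared to incident MITT users". No censoring weight is mentioned.
- **Sensitivity analyses (8.7.3.3).** There are three: a stricter COPD definition, a 14-day entry overlap for MITT, and a 1,440-day cap. "When one of the 3 conditions are applied, other 2 conditions will not be applied but original conditions will be kept".
- **Follow-up length (8.3.3.2).** It is tabulated by group to show any difference.
- **Limitations (8.9).** The reason why prescriptions cease is unknown. Internal validity is said to depend on the limitations affecting both groups similarly.

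**The concern.** A Trelegy 100 user has one product that can lapse. A MITT user leaves follow-up when any component lapses long enough to end the overlap, so MITT follow-up may be shorter. Age, home oxygen, prior CAP and prior exacerbation could plausibly affect both stopping and CAP.

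If high-risk patients leave one group faster than the other, the patients still at risk stop being comparable, even when the weighting balanced them perfectly at index. Weights fixed at index cannot repair that, and the baseline balance table in 8.7.3.2.3 cannot show it. The HR would then no longer be the marginal HR that the protocol names.

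The study reads the HR against 3. An upward shift could create a signal and a downward shift could hide one.

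**Working it through.** **1. Does any planned analysis change the stop rule?** The COPD-definition analysis changes who enters. The 14-day analysis changes what counts as MITT at entry. The 1,440-day analysis changes only the cap, so patients are exposed to the same censoring for longer. The answer is no.

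**2. Reproduce Table 1 (8.5.1).** With N1 Trelegy 100 users, N2 MITT users and annual rate r:

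E = (N1+N2)·r; E1 = E·N1·HR/(N1·HR+N2); E2 = E−E1; SE = √(1/E1+1/E2); P = 1−Φ((ln 3−ln HR)/SE).

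For 3225/2185, r = 8%, HR 2.5: E = 432.8, E1 = 340.5, E2 = 92.3, SE = 0.1174, z = 0.1823/0.1174 = 1.553, P = 6.0%, as printed. This formula matches all 40 cells.

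**3. How far can censoring move the HR?** The protocol gives no discontinuation rates, so every stopping input here is assumed. Take two risk classes in the same proportions in both groups (perfect balance at index). Let w be the class share, λ the class CAP hazard (multiplied by the true HR under Trelegy 100) and d the stopping hazard by group and class. Then:

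- on-treatment share: Y_g(t) = Σ w·exp(−CAP hazard·t − accumulated stopping hazard);
- event density: e_g(t) = the same sum with each term multiplied by its CAP hazard;
- the treatment-only Cox estimate tends to the b that solves ∫{e1 − (e1+e0)·Y1·exp(b)/(Y1·exp(b)+Y0)}dt = 0, with Y and e scaled by group size.

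The factor is exp(b) divided by its value without stopping.

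Assumed moderate inputs: 30% high-risk with 3 times the CAP hazard, CAP 10% per year, no stopping before day 60, then 0.8 per year (Trelegy 100) and 1.5 per year (MITT), end at 360 days, 1935/1311 users, true HR 1.

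| Stopping pattern | Factor |
|---|---|
| Level differs only (0.8 v 1.5) | 1.00 |
| Same risk-dependent rates in both groups (0.8 low, 1.6 high) | 1.00 |
| High-risk stop 2× as fast in both, levels 0.8 v 1.5 | 1.03 |
| High-risk stop 2× as fast, MITT only | 1.08 |
| High-risk stop 3× as fast, MITT only | 1.14 |
| High-risk stop 2× as fast, Trelegy 100 only | 0.95 |
| High-risk stop half as fast, MITT only | 0.95 |

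At true HR 2.5 these change by no more than about 0.01. Stronger assumptions go further. Tripling in Trelegy 100 only gives 0.92. A second set (8% per year, no minimum period, risk ratio 3 or 5) gives:

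- 1.00–1.01 when only the level differs, or when the pattern is identical in both groups;
- 1.03–1.17 when high-risk patients stop at twice the rate in both groups and MITT stops 1.4 to 3 times as often;
- 1.10–1.40 when the dependence is in MITT only (2× to 4×);
- 0.86–0.91 when the dependence in MITT is reversed.

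**4. Effect on the HR > 3 reading.** Put true HR × factor into the step 2 formula at the 8% rate:

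| True HR × factor | 3225/2185 | 1935/1311 |
|---|---|---|
| 2 × 1.10 = 2.20 | 0.0% → 0.3% | 0.2% → 1.7% |
| 2.5 × 1.10 = 2.75 | 6.0% → 23.5% | 11.4% → 28.8% |
| 3.5 × 0.95 = 3.325 | 88.1% → 78.9% | 82.0% → 73.3% |
| 3.5 × 0.90 = 3.15 | 88.1% → 65.1% | 82.0% → 61.8% |

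The 0.90 row lies outside the moderate range and inside the wider one.

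**5. Do censoring weights help?** In 400 simulated studies of 3,246 patients under the moderate inputs, with dependence in MITT only (2× and 3×), the mean HR was 1.09 and 1.13 without censoring weights. With them it was 1.00 and 1.02. In the milder case the SD of log HR rose from 0.143 to 0.170 (unstabilised weights).

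**The case against.** - **The rule is largely the same for both groups.** They share the grace period and the gap rule, and a switch of components is not a stop. Overlap is simply what being on triple therapy means, and easier persistence on one inhaler is a real difference between the treatments. This stands: the rule is a fair on-treatment definition and should be kept.
- **A reader might infer that the stricter MITT rule itself biases the HR, or that the HR is biased upward.** The documents support neither. A difference in level alone gives 1.00–1.01. Bias also needs stopping that depends on CAP risk, and the protocol neither quantifies this nor indicates its direction.
- **The threshold of 3 already leaves room for residual confounding (8.5.1).** This stands for true HRs of 2 or below. It does not help between about 2.5 and 3.5, where Table 1 itself shows the reading is sensitive.
- **Unequal follow-up is anticipated.** It is tabulated and compared (8.3.3.2, 8.7.3.2.2), and unknown stop reasons are disclosed (8.9). These steps describe the problem and do not correct it.
- **Details belong to the SAP (8.7).** This stands in part. However, the protocol itself fixes the censoring rule, the weights and a closed list of three conditions. That treatment is the only model term is a reading of the marginal HR; 8.7.3.1.1 does not say so.

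**Conclusion.** The point holds as a possible bias, not a demonstrated one. The primary HR is protected against selection at index but not against selection through discontinuation, and no planned analysis would reveal the difference. Bias requires that stopping depends on CAP risk factors and that it differs between groups in level or pattern. Under moderate assumed inputs the factor is about 0.95 to 1.14; stronger assumptions widen it to about 0.86 to 1.40. The effect on the HR > 3 reading is material mainly for true HRs of about 2.5 to 3.5. This merits an added sensitivity analysis and does not invalidate the base case.

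**What to change.** Keep the on-treatment base case. Add one sensitivity analysis to 8.7.3.3: multiply the treatment weight by stabilised inverse-probability-of-censoring weights for discontinuation, fitted separately in each group from the 8.3.3.1 covariates. Report discontinuation by group alongside the follow-up-length table.

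The cost is a short addition to the text and one further model on data already collected. The interval will be somewhat wider, and only measured covariates are corrected.

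An as-started analysis is optional and supportive only. It should end at the last database record, and agreement with it should not be a condition for calling the conclusion robust. Section 8.9 says that patients may move to hospitals outside the database, where pneumonia is not seen. Following everyone to 360 days would count them as event-free, more often in the group that stops more. With stop rates of 0.8 and 1.5 per year after day 60 (assumed), the mean share of time after stopping is about 0.223 for Trelegy 100 and 0.355 for MITT. If a fraction f of those who stop leave the database, a true HR of 1 appears as about (1−0.223f)/(1−0.355f): 1.04, 1.08 and 1.13 for f = 25%, 50% and 75%. That is as large as the bias it would be meant to check.

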## 8.2. Study Population and Setting

COPD patients who meet the inclusion and exclusion criteria.

### 8.2.1. Inclusion criteria

To be included in the study population, patients must meet all of the following criteria:

- Aged 40 years or older on the index date  
As 96% of the patients with COPD were aged 40 years or older in the Ministry of Health, Labour and Welfare (MHLW)'s Patient Survey (2017), the target of this study was set at patients aged 40 years or older.
- Patients with records of ICD-10 codes for COPD (J42, J43 or J44), one record at the index date and additional 2 records (outpatient visit or hospital admission) in the 360 days look-back period [index date, index date -360 days]. This criterion is to exclude patients with infrequent visits who may not be COPD patients, and to secure, collection of patient characteristics data in the look-back period.
- At least one record (outpatient visit or hospital admission) with any ICD-10 codes in the 180 days prior to the start date of look-back period [index date – 360 days, index date – 540 days]. This criterion is to secure patient records throughout the look-back period.
- Two study populations will be set up in Trelegy 100 and MITT users, respectively; COPD patients who started Trelegy 100 or MITT between May 22, 2019 and May 5, 2022 (overall users), and subpopulations of the overall users without any triple therapies in the 360-day look-back period (incident users). Pneumonia occurrence in overall users as well as incident users will be calculated to have good generalizability of study results, since incident users will be a part of overall users. The first use of Trelegy 100 or MITT in the identification period will be included as overall cases. The index date for MITT overall users will be the first prescription date after the launch date of Trelegy 100 (May 22, 2019). In the identification of incident users, “any triple therapies in the look-back period” refer to triple therapies with only COPD indication, mixture of COPD and asthma indications, and only asthma indication.

## 8.2.2. Exclusion criteria

Patients who meet any of the following criteria are excluded from the study population:

- Patients without any record of COPD diagnosis from May 22, 2019 to May 5, 2022. Patients hospitalized within 30 days before the index date by “hospitalization due to CAP” by the same definition as the Outcome definitions (Sec 8.3.2). This criterion is to exclude cases of readmission of “hospitalization due to CAP” and nosocomial infection.

[figure not shown]

Figure2 Schematic diagram: Cohort selection of primary endpoint

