**Definition of terms**

Term	Definition
Terms related to study design	
Study design	Study methods of choice in light of research questions. e.g., cohort design and nested case-control design
Terms for target population	
Exclusion criteria	Criteria to exclude from the target population
Inclusion criteria	Criteria for inclusion in the target population
Study population	Scope of the study group is defined by inclusion and exclusion criteria by combining information on the attributes of the study population (age, gender, presence of disease, use of drugs, etc.), location (medical institutions, etc.), time (date and time information, etc.).
Terms for duration	
At risk	Condition in which the outcome of interest can occur
Exposure period	Period starting at the index date and ending at 30 days (grace period) after the end date of the final prescription
Follow-up period	Duration of follow-up to confirm the presence or absence of an outcome in each case
Gap	Period between the prescription periods
Grace period	Period in which we consider prescription to be continuing
Index date	Key date for design: Date of start of treatment
Look-back period	Period for each covariate to be measured
Observational period	Period within which each case can be observed within the data source used
Prescription period	Period from the date of prescription until the end of treatment estimated from the package insert
Study period (data period)	Period of data extracted from the database
Terminology for analysis	
Base case analysis	Analysis to determine the results corresponding to the objective of the study
Exploratory analysis	Analysis to determine the results corresponding to the exploratory objectives
Data review	Data review performed to confirm the certainty of the code used in the definition
Sensitivity analysis	Analysis performed to confirm the robustness of the analysis results
Other	
Validation study	In the secondary use of data, the validity of the information contained in the data should be investigated in agreement with other reliable sources. Algorithms that extract specific cases, especially for injury and disease name codes, from the data are often investigated.

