### 8.3.2. Outcome definitions

#### 1. Algorithm of outcome definitions

- Hospitalization due to CAP which occurs 1 day or more after the index date. Admission date will be treated as the first day of hospitalization due to CAP.

Hospitalization due to CAP during follow-up period (defined in 8.1 Study Design) will be identified using DPC data. ICD-10 codes, DPC disease segments, prescription data and diagnostic imaging data will be used as follows.

#### Definition 1

- 1) Any of the ICD-10 codes of J10.0, J11.0 or J12-J18
- 2) The above ICD-10 codes in DPC disease segment #21 (disease which triggered the hospitalization)
- 3) Prescription of antibiotics (ATC code: J01) on the day of admission or the next day of hospitalization
- 4) Diagnostic imaging (X-ray or computerized tomography (CT) scan) conducted between 2 days before and 7 days after the hospitalization

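### A CAP admission on the index date is neither excluded by a listed criterion nor counted as an outcome, so a later readmission can count as a first event

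*Protocol*

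**What the plan says.** Four statements in the protocol fix the boundary at time zero.

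- **Exclusion (Section 8.2.2).** The criterion removes "Patients hospitalized within 30 days before the index date by" a CAP hospitalization that meets the outcome definition. Its stated aim is to keep out readmissions for CAP and nosocomial infection.
- **Outcome (Section 8.3.2).** The endpoint is "Hospitalization due to CAP which occurs 1 day or more after the index date". For dating, "Admission date will be treated as the first day of hospitalization due to CAP".
- **Follow-up (Section 8.1, text under Figure 1).** "Follow-up period will be from the index date (including the index date) to the earliest date of the followings": CAP admission, death, end of exposure, or 360 days.
- **Who is followed (Section 8.1).** The hazard ratio is to be estimated by "identifying and following patients without the pneumonia event at the index date (at risk"). The definition of terms explains at risk as "Condition in which the outcome of interest can occur".

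The index date is the first prescription of Trelegy 100 or multiple inhaler triple therapy (MITT) in the identification period (Section 8.3.1). No criterion confines that prescription to outpatients, and Section 8.4 says that the database holds inpatient prescriptions. Starting triple therapy on the day of a CAP admission is therefore possible under the stated rules.

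**The concern.** The exclusion window ends the day before the index date and the outcome window opens the day after it, while follow-up already runs on the index date. A CAP admission on that day falls between the two windows. The patient enters the cohort with active pneumonia. If discharged and readmitted with pneumonia, the patient supplies an event that is really a recurrence, which is what the 30-day criterion was written to prevent.

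At stake are the CAP incidence rates in both groups (secondary objective a) and, if such starts are more common in one group, the primary hazard ratio. There is also a reproducibility problem: two programmers working from this text could build different cohorts.

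**Working it through.** **1. One day axis (day 0 = index date), base case.**

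- Days -30 to -1: a CAP hospitalization excludes the patient (8.2.2).
- Day 0: no listed exclusion; a CAP admission is not an outcome (8.3.2); follow-up is running (8.1).
- Day 1 up to day 360: a CAP admission is an outcome.

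**2. Three patients, each first prescribed triple therapy on day 0.**

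- CAP admission on day -1: excluded.
- CAP admission on day 0: kept, no event.
- CAP admission on day 1: kept, event.

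The middle patient is as ill as the first at time zero but is handled as free of pneumonia. If that patient goes home and is readmitted with pneumonia while still exposed, the readmission is the first hospitalization to satisfy 8.3.2 and is scored as the event.

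**3. Stays still running at index.** Section 8.2.2 does not say whether its window is tested on the admission date or on days in hospital. If it uses the admission date, by which 8.3.2 dates the event, a CAP stay that began more than 30 days earlier and is still running on day 0 also passes. If it uses days in hospital, that stay is caught.

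**4. Covariate side effect.** Section 8.2.1 writes the look-back window as including the index date. A day-0 CAP admission could therefore be recorded as history of pneumonia while the same patient is followed as free of it.

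**5. Illustrative size.** The documents give no share of patients starting on the day of a CAP admission (g) and no readmission proportion (r). Both are assumptions here: g = 0.5% to 5%, r = 10%. Users and expected events at 80 per 1000 patient-years come from Tables 4 and 5: 3225 users and 258 events for Trelegy 100, 2185 users and 175 events for MITT.

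Readmissions scored as first events = users × g × r.

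- g = 1%: 3225 × 0.01 × 0.10 = 3.2, and 2185 × 0.01 × 0.10 = 2.2. Each is about 1.25% of expected events (3.2/258, 2.2/175).
- g = 0.5%: 16 patients and 1.6 readmissions (Trelegy 100); 11 and 1.1 (MITT).
- g = 5%: 161 patients and 16.1 readmissions (Trelegy 100); 109 and 10.9 (MITT).

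Effect on the crude rate ratio:

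- Equal g in both groups: (261.2/258) / (177.2/175) = 1.0125/1.0125 = 1.00.
- All in one group at g = 1%: 261.2/258 = 1.012.
- All in one group at g = 5%: 274.1/258 = 1.062.

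The standard error of the log hazard ratio is about sqrt(1/258 + 1/175) = 0.098. The one-sided shifts are ln(1.0125) = 0.012 and ln(1.0625) = 0.061, or about 0.13 and 0.62 standard errors. These are unweighted approximations, and the tables assume one patient-year per patient, so actual event counts may be lower.

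**The case against.** **Section 8.1 already states the rule.** It says that patients without the pneumonia event at index are followed, which can be read as closing day 0. The intent is indeed clear. But Section 8.7.2 takes eligibility from Section 8.2, and nothing listed there carries the intent out.

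**The 30-day wording might include day 0.** That is possible. Yet where the protocol means to include the index date it says so, in the look-back window and in the start of follow-up. Here it does not.

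**Figure 2 or the analysis plan may settle it.** Neither is available, and no fault is drawn from that. The criterion itself is fixed in the protocol text, so the clarification belongs there.

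**The stopping rule could end follow-up on day 0.** If a day-0 admission triggers the CAP stopping clause, the patient contributes one day and no event, and no readmission is scored. That reading is available, but it conflicts with 8.3.2, under which a day-0 admission is not an outcome. It also leaves the patient in the cohort.

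**A stronger reading.** A reader might infer that everyone who starts treatment in hospital is wrongly followed until discharge, because a CAP admission cannot occur meanwhile, and that risk time must start at discharge. The documents do not support this as a required change:

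- Starting at discharge makes entry depend on surviving, and staying on treatment, until discharge. That selection could itself differ between groups.
- Later non-CAP stays would remain in risk time, so the at-risk definition would still not be met throughout.
- The effect is small even on extreme assumptions. With 5% of Trelegy 100 and 20% of MITT users starting in hospital, 20 days remaining and a mean follow-up of 180 days, the rate-ratio factor is (1 - 0.05 × 20/180) / (1 - 0.20 × 20/180) = 0.9944/0.9778 = 1.017. That is ln(1.017)/0.098, under 0.2 standard errors.

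**Conclusion.** The gap on the index date is real on the text. A same-day CAP admission is neither excluded by a listed criterion nor counted, against both the design statement in Section 8.1 and the stated purpose of Section 8.2.2. Whether a CAP stay of more than 30 days still running at index is excluded is ambiguous rather than wrong.

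The effect is probably small and cannot be sized from the documents. On the assumed proportions it ranges from about 2 to 16 misclassified events in the larger Trelegy 100 scenario. It leaves the hazard ratio essentially unchanged if same-day starts are equally common in both groups. A reader might infer that the primary conclusion is at risk. The documents do not support that: even the one-sided 5% case moves the ratio by about 6%, against a signal threshold of HR > 3. The case for the change is that the protocol contradicts itself and the repair is nearly free.

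**What to change.** Reword Section 8.2.2 to exclude patients with a hospitalization due to CAP, by the definition in Section 8.3.2, whose stay includes any day from index date -30 through the index date inclusive. This covers same-day admissions and CAP stays still running at index. Apply it identically to Trelegy 100 and MITT users.

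The cost is one sentence in the protocol and one programming rule on the dates of the stay. The downside is the loss of a small number of patients.

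Optionally, report by group the share of index prescriptions written during a hospital stay. This is descriptive only. The start of risk time need not change.
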